## 5.5. Pharmacokinetic Assessments

The PK samples will be collected for both treatment groups to maintain the blind. The PK samples obtained from the ETX2514SUL group will be analyzed (using a validated assay) by a central bioanalytical laboratory.

The PK plasma samples will be used to estimate PK parameters using non-compartmental methods, such as area under the concentration-time curve (AUC), maximum plasma concentration, time to maximum plasma concentration, drug clearance, half-life, minimum plasma concentration, and steady-state volume of distribution for ETX2514SUL. Population PK and PK-pharmacodynamic modeling will be performed and reported separately. The results will not be included in the clinical study report.

## 6. EFFICACY ENDPOINTS

### 6.1. Primary Endpoints

The primary efficacy parameter is the proportion of patients with an overall success (clinical cure and microbiologic eradication) in the m-MITT Population at the TOC Visit.

### 6.2. Secondary Endpoints

The secondary efficacy parameters include the following:

Proportion of patients with a response of clinical cure in the MITT, m-MITT, CE and ME Populations at the TOC Visit; and

Proportion of patients with a response of microbiologic eradication in the m-MITT and ME Populations at the TOC Visit.

### 6.3. Exploratory Endpoints

The exploratory efficacy parameters include the following:

- Proportion of patients with a response of sustained microbiologic eradication in the m-MITT and ME Populations at the LFU Visit,
- Proportion of patients with a response of sustained clinical cure in the MITT, m-MITT, CE, and ME Populations at the LFU Visit,
- Proportion of patients with a response of clinical cure in the MITT and m-MITT Populations at Day 5,
- All-cause mortality through the LFU Visit in the MITT Population,
- Summary (number and percentage of patients) of the assessment of clinical signs and symptoms of cUTI and AP at each time point throughout the study by treatment group in the MITT Population, and
- Descriptive statistics of the length of hospital stay by treatment group for the MITT Population.

## **7. ANALYSIS POPULATIONS**

The following analysis populations will be included in the analyses.

### **7.1. Intent-to-Treat Population**

The Intent-to-Treat (ITT) Population will include all patients randomized to study drug treatment (ETX2514SUL or placebo) regardless of whether the patient actually receives study drug.

### **7.2. Modified Intent-to-Treat Population**

The Modified Intent-to-Treat (MITT) Population will include patients who meet ITT criteria and receive any amount of study drug.

### **7.3. Microbiologically Modified Intent-to-Treat Population**

The Microbiologically Modified Intent-to-Treat (m-MITT) Population will include patients who meet MITT criteria and have at least 1 baseline uropathogen from an appropriately collected pre-treatment baseline urine or blood sample. To be considered a pathogen, the baseline urine culture must grow 1 or 2 bacteria isolates, each at  $\geq 10^5$  CFU/mL. If  $\geq 3$  bacterial isolates are identified, the culture will be considered contaminated regardless of colony count unless 1 of the isolates, even if the CFU/mL is  $< 10^5$ , that grows in the urine is also isolated from a blood culture obtained within 48 hours before the start of administration of the first dose of study drug. If the same pathogen is present in both blood and urine cultures, even if the CFU/mL is  $< 10^5$  in the urine, the organism will be considered a pathogen.

The m-MITT Population will be the primary efficacy population.

### **7.4. Clinically Evaluable Population**

The Clinically Evaluable (CE) Population will include patients who meet the MITT criteria and meet evaluability criteria (meet key inclusion criteria, do not have key exclusion criteria, received a minimum of at least 12 doses of IV treatment to be a clinical cure [at least 8 doses of IV treatment to be a clinical failure], received  $\geq 80\%$  of anticipated doses, did not have a clinical response of indeterminate at the TOC visit).

## **7.5. Microbiologically Evaluable Population**

The Microbiologically Evaluable (ME) Population will include patients who meet m-MITT criteria and CE criteria and have an appropriately collected urine culture specimen and interpretable urine culture result at the TOC Visit.

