4.3 Withdrawal Criteria

Participation of a patient in this clinical study may be discontinued for any of the following reasons:

- The patient withdraws consent or requests discontinuation from the study for any reason;
- Occurrence of any medical condition or circumstance that exposes the patient to substantial risk and/or does not allow the patient to adhere to the requirements of the protocol;
- Any SAE, clinically significant adverse event, severe laboratory abnormality, intercurrent illness, or other medical condition which indicates to the Investigator that continued participation is not in the best interest of the patient;
- Pregnancy;
- Requirement of prohibited concomitant medication;
- Patient failure to comply with protocol requirements or study-related procedures; or
- Termination of the study by the Sponsor or the regulatory authority.

For patients in whom the creatinine clearance drops below 70 mL/min after baseline, the Investigator should repeat serum creatinine at the local laboratory once they receive the abnormal laboratory result to confirm the value. The Investigator may withdraw the patient from the study when a dose adjustment for imipenem is necessary or when patient safety is at risk. However, if the Investigator believes that the creatinine clearance decrease is not clinically significant or will quickly reverse, the Medical Monitor will be contacted to discuss if the patient may continue in the study or should be withdrawn.

If a patient withdraws prematurely from the study due to the above criteria or any other reason, study staff should make every effort to complete the full panel of assessments scheduled for the EOT Visit, and the patient should be followed through the LFU Visit. If a patient withdraws after the EOT Visit, study staff should make every effort to complete the full panel of assessments scheduled for the study visit following the date of withdrawal (TOC Visit or LFU Visit), as applicable. The reason for subject withdrawal must be documented in the electronic case report form (eCRF).

In the case of patients lost to follow-up, attempts to contact the subject must be made and documented in the patient's medical records.

Withdrawn subjects will not be replaced.

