6.4 Test-of-Cure Visit

The TOC Visit will occur 7 days (± 1 day) after the EOT Visit.

The following procedures will be performed at the TOC Visit:

- Record concomitant medications;
- Perform a limited physical examination;
- Obtain vital signs, including blood pressure, heart rate, and respiratory rate;
- Assess clinical signs and symptoms;
- Assess clinical outcome;

Note: if a patient is a clinical failure at EOT, the patient is automatically considered a failure at the TOC and LFU Visits, and the assessment of clinical response by the Investigator should be listed as “failure at EOT.”

- Collect blood samples for:
 - Serum chemistry;
 - Hematology; and
 - Blood cultures, if applicable;
- Collect urine sample by clean-catch midstream or other appropriate method that minimizes risk of bacterial contamination for:
 - Urinalysis; and
 - Urine cultures; and
- Assess adverse events.

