9 STATISTICS

9.1 Analysis Populations

The Intent-to-Treat (ITT) Population will include all patients randomized to study drug treatment (ETX2514SUL or placebo) regardless of whether the patient actually receives study drug.

The MITT Population will include patients who meet ITT criteria and receive any amount of study drug.

The m-MITT Population will include patients who meet MITT criteria and have at least 1 baseline uropathogen from an appropriately collected pre-treatment baseline urine or blood sample. To be considered a pathogen, the baseline urine culture must grow 1 or 2 bacteria isolates, each at $\geq 10^5$ CFU/mL. If ≥ 3 bacterial isolates are identified, the culture will be considered contaminated regardless of colony count unless 1 of the isolates, even if the CFU/mL is $< 10^5$, that grows in the urine is also isolated from a blood culture obtained within 48 hours before the start of administration of the first dose of study drug. If the same pathogen is present in both blood and urine cultures, even if the CFU/mL is $< 10^5$ in the urine, the organism will be considered a pathogen.

The CE Population will include patients who meet the MITT criteria and meet evaluability criteria (meet key inclusion criteria, do not have key exclusion criteria, received a minimum of at least 12 doses of IV treatment to be a clinical cure [at least 8 doses of IV treatment to be a clinical failure], received $\geq 80\%$ of anticipated doses, did not have a clinical response of indeterminate at the TOC visit).

The ME Population will include patients who meet m-MITT criteria and CE criteria and have an appropriately collected urine culture specimen and interpretable urine culture result at the TOC Visit.

The Primary Efficacy Population is the m-MITT Population.

The Safety Population will include patients who meet ITT criteria and receive any amount of study drug. All safety analyses will be based on actual treatment received.

The PK Population will include patients who meet MITT criteria and have at least 1 plasma PK sample drawn.

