##### **5.1.2. Clinical Outcome**

Based on the assessment of signs and symptoms, the Investigator will choose 1 of the following clinical outcomes at the Day 5, EOT, and TOC Visits:

Clinical cure: complete resolution or significant improvement of signs and symptoms of cUTI or AP that were present at baseline and no new symptoms, such that no further antimicrobial therapy is warranted.

Clinical failure: symptoms of cUTI or AP present at study entry have not significantly improved or completely resolved, or new symptoms of cUTI or AP have developed and require the initiation of a non-study antibacterial drug therapy, or death.

Clinical indeterminate: insufficient data are available to determine if the patient is a cure or failure.

Based on the assessment of signs and symptoms, the Investigator will choose 1 of the following clinical outcomes at the LFU Visit:

Sustained clinical cure: met criteria for clinical cure at the TOC Visit and the LFU Visit.

Relapse: clinical cure at the TOC Visit but signs and symptoms of cUTI or AP are present at the LFU Visit.

Clinical failure: clinical failure at the TOC Visit carried forward to the LFU Visit or death between the TOC Visit and LFU Visit.

Clinical indeterminate: insufficient data are available to determine if the patient is a sustained clinical cure or clinical relapse.

Note: if a patient is a clinical failure at EOT, the patient is automatically considered a failure at the TOC and LFU Visits, and an assessment of clinical response by the Investigator will be listed as “failure at EOT.”

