#### **5.1.4. Microbiologic Outcome**

##### **5.1.4.1. Per-Pathogen Microbiologic Outcome**

Microbiologic outcome at Day 5, EOT, and TOC will be programmatically determined for each pathogen isolated at baseline. Per-pathogen microbiological response categories are eradication, persistence, and indeterminate defined as following:

Microbiologic eradication: the demonstration that the baseline bacterial pathogen(s) is reduced to  $< 10^4$  CFU/mL according to the Food and Drug Administration (FDA) criteria and  $< 10^3$  CFU/mL according to the European Medicines Agency (EMA) criteria on urine culture and negative on repeat blood culture (if positive at baseline).

Microbiologic persistence: the urine culture grows  $\geq 10^4$  CFU/mL for the FDA ( $\geq 10^3$  CFU/mL for the EMA) of any of the baseline pathogen(s) identified at study entry and/or a blood culture demonstrates the same baseline pathogen(s). Patients who are a persistence at EOT will be considered a persistence at TOC.

Microbiologic indeterminate: no follow-up urine culture is available, or the follow-up urine culture cannot be interpreted for any reason, or the follow-up urine culture is considered contaminated. For a baseline blood pathogen, no follow-up blood culture is available.

A per-pathogen microbiological outcome will be determined at the LFU visit. Per-pathogen microbiological outcome categories are sustained eradication, presumed sustained eradication,

continued persistence, recurrence, and indeterminate. A per-pathogen microbiologic outcome of persistence at TOC will be considered a continued persistence at LFU defined as following:

Sustained microbiologic eradication: microbiologic eradication at the TOC Visit and the LFU Visit.

Presumed sustained microbiologic eradication: no urine culture was done at LFU and patient meets clinical criteria for sustained clinical cure.

Microbiologic continued persistence: a per-pathogen microbiologic outcome of persistence at the TOC Visit will be considered a continued persistence.

Microbiologic recurrence: urine culture grows  $\geq 10^4$  CFU/mL for the FDA ( $\geq 10^3$  CFU/mL for the EMA) of any of the baseline pathogen(s) identified at study entry and/or a positive blood culture at any time after documented eradication at the TOC Visit up to and including the LFU Visit.

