## **8.2. Handling of Dropouts/Missing data**

For the primary efficacy outcome measure of overall response, patients with missing data or who are lost to follow-up will be considered as an indeterminate response and are included in the denominator for the calculation of overall success rate. Thus, patients with an indeterminate outcome are considered as failures for the primary analysis. A clinical failure occurring at an earlier time point will be carried forward to the subsequent visits.

In cases of missing or incomplete dates (e.g. AE and concomitant medications), the missing component(s) will be assumed as the most conservative value possible. For example, AEs with missing start dates, but with stop dates either overlapping into the treatment period or missing, will be counted as treatment-emergent, taking the worst-case approach. When partial dates are present in the data, both a partial start date and/or a partial stop date will be evaluated to determine whether it can be conclusively established that the AE started prior to the start of study drug or ended prior to the start of study drug. If the above cannot be conclusively established based on the partial and/or present dates, then the AE will be considered as treatment-emergent. Actual data values as they appear in the original eCRF will be presented in the data listings.

Missing values for other variables will not be imputed and only observed values will be used in data analyses and summaries.

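### Should the ME population keep patients whose TOC failure is already fixed when their TOC urine culture is missing?

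*SAP*

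**What the plan says.** The ME definition is the same in both documents. Protocol 9.1 states: "The ME Population will include patients who meet m-MITT criteria and CE criteria and have an appropriately collected urine culture specimen", and SAP 7.5 gives the culture condition in full: patients must "have an appropriately collected urine culture specimen and interpretable urine culture result at the TOC Visit". Neither makes an exception.

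Three other rules settle a TOC outcome without a TOC culture:

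- SAP 8.2: "A clinical failure occurring at an earlier time point will be carried forward to the subsequent visits". Protocol 6.4 says the same for EOT: "if a patient is a clinical failure at EOT, the patient is automatically considered a failure at the TOC and LFU Visits".
- SAP 5.1.2 includes death in clinical failure; the definition ends "new symptoms of cUTI or AP have developed and require the initiation of a non-study antibacterial drug therapy, or death".
- SAP 5.1.4.1: "Patients who are a persistence at EOT will be considered a persistence at TOC".

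Under SAP 5.1.5, either clinical failure or persistence is enough for overall failure. CE (SAP 7.4) needs at least 8 doses for a clinical failure, at least 80% of anticipated doses, and that the patient "did not have a clinical response of indeterminate at the TOC visit". It does not need a TOC culture.

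ME is used for overall success (SAP 8.11.1), and for clinical cure and microbiologic eradication (SAP 8.11.3). The last two are listed secondary endpoints in SAP 6.2.

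**The concern.** A clinical failure carried forward from EOT is not indeterminate at TOC, so the patient can be in CE. The overall outcome is known to be failure whatever a TOC culture would show, yet without that culture the patient leaves ME. For persistence at EOT the point is sharper still, because the TOC urine culture cannot improve the scored microbiologic outcome.

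If patients who have failed and moved to other treatment return for the TOC culture less often than cured patients, ME loses failures selectively. Overall success and clinical cure in ME would then read too high, and unequal loss between arms would shift the treatment difference. Eradication would be affected only through persistence at EOT, since a clinical failure with no culture is microbiologically indeterminate.

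**Working it through.** The plan gives no figure to reproduce: no power calculation, assumed success rate or missing-culture rate. Every rate and ME size below is an assumption.

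**Who is affected.** Three groups need separating.

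1. *Carried-forward clinical failures and deaths before TOC.* Losing them raises ME overall success and ME clinical cure.
2. *Persistence at EOT with a known TOC clinical outcome.* Losing them raises overall success and eradication. If the patient was a clinical cure, the loss lowers ME clinical cure: with 30 cures in 35, dropping one such patient moves 30/35 = 85.7% to 29/34 = 85.3%. With no TOC clinical outcome and no carried-forward failure, the patient is clinically indeterminate and already outside CE.
3. *Failures stopped early.* SAP 7.4 does not say what the anticipated doses are. If they are the planned 28, the threshold is 0.8 × 28 = 22.4, so 23 doses, and failures stopped before then leave at CE rather than ME. Under the elapsed-time rule for compliance in SAP 8.10 they could stay in CE.

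**Bias under the current rule.** Let p be true success, k the share of failures fixed before TOC, f the culture loss in fixed failures, and s the culture loss in everyone else.

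Observed rate = p(1−s) / [p(1−s) + (1−p)k(1−f) + (1−p)(1−k)(1−s)]

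**Rate with an exception for fixed failures.** They always stay, so (1−f) becomes 1:

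Rate = p(1−s) / [p(1−s) + (1−p)k + (1−p)(1−k)(1−s)]

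With p = 0.80 and k = 0.50:

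| Loss: fixed failures v others | Current rule | With exception |
|---|---|---|
| 10% v 10% | 0.72/0.90 = 80.0% | 0.72/0.91 = 79.1% |
| 25% v 10% | 0.72/0.885 = 81.4% | 0.72/0.91 = 79.1% |
| 10% v 25% | 0.60/0.765 = 78.4% | 0.60/0.775 = 77.4% |
| 50% v 0% | 0.80/0.95 = 84.2% | 0.80/1.00 = 80.0% |

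The denominator would be 1−s if loss were equal. The current rule moves it down by (1−p)k(f−s); the exception moves it up by (1−p)k·s. So the exception is nearer the truth only when f exceeds roughly twice s. At 25% v 10% the errors are +1.4 and −0.9 points, a gain of about half a point. At equal loss the current rule is exact and the exception is not.

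**Other values of k, current rule.** At 25% v 10%: 80.7% (k = 25%) and 82.8% (k = 100%). At 50% v 0%: 82.1% and 88.9%.

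**Treatment difference.** For true rates of 80% and 70% (10.0 points) with k = 50% in both arms:

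- 25% v 10%: 81.36 − 71.79 = 9.6 points.
- 50% v 0%: 84.21 − 75.68 = 8.5 points.

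**Against the precision available.** With 32/40 and 16/20 in ME, the continuity-corrected 95% half-width is 1.96 × √(0.16/40 + 0.16/20) + 0.5 × (1/40 + 1/20) = 25.2 points. Losing one fixed failure moves the placebo arm from 16/20 = 80.0% to 16/19 = 84.2%; losing one cure moves it to 15/19 = 78.9%. That shows how small the arm is, not that the rule is biased.

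**The case for a change.** The case for changing the rule is not empty. The documents offer a route by which failures could be lost. Protocol 5.5.1 prohibits most non-study antibiotics for the infection, Protocol 4.3 lists the need for a prohibited medication as a reason to discontinue, and Protocol 6.6 gives a patient withdrawn before completing study drug an EOT Visit at termination. The urine specimen taken at on-therapy failure does not satisfy the TOC condition. Protocol 3.1 describes follow-up after stopping dosing as being for safety. Deaths before TOC are certain to lack the culture. If loss were as unequal as 50% v 0%, the exception would remove an error of 4.2 points at the cost of about one sentence.

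The mechanism stands, and so does the loss of deaths. General excess loss among failures does not. Protocol 6.4 schedules a urine culture at TOC for everyone and places its failure-at-EOT note inside that visit. For withdrawn patients Protocol 4.3 asks for the EOT assessments "and the patient should be followed through the LFU Visit". Deaths before TOC should be few, because Protocol 4.1 requires expected survival and Protocol 4.2 excludes severe sepsis.

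The exception also costs more than a sentence. It would admit clinical failures with no microbiologic outcome, which then have to be left out of the eradication denominator. Membership would also differ between the FDA and EMA thresholds, since persistence at EOT is defined under both.

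**Conclusion.** Keep the ME definition. The gap is real, but requiring the culture from everyone is a fair trade-off: it applies the same entry condition to cures and failures and is unbiased for overall success when cultures are missed regardless of outcome. The alternative keeps fixed failures without cultures while still dropping cures without them, so it reads low whenever any cures miss the culture.

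Under the assumed 80% success and k = 50%, the current rule errs by +1.4, 0.0 or −1.6 points at losses of 25% v 10%, 10% v 10% and 10% v 25%; the exception errs by −0.9, −0.9 and −2.6. The current rule does clearly worse only under strongly unequal loss, for which the documents give no evidence.

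Little depends on it. The primary objective is safety, and Protocol 9.2 makes the efficacy analyses descriptive. Overall success, clinical cure and eradication are all reported in m-MITT, which needs no TOC culture; clinical cure is also reported in CE, which needs none either. SAP 8.4 tabulates the reasons for exclusion from ME by arm and lists them by patient, so any imbalance will be visible. If that listing shows several fixed failures lost, an analyst can add a supportive table that puts them back, noting that it reads low when cures also miss cultures.

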## **7.6. Safety Population**

The Safety Population will include patients who meet ITT criteria and receive any amount of study drug. All safety analyses will be based on actual treatment received.

# **8. STATISTICAL ANALYSIS**

## **8.1. General Statistical Considerations**

Summary statistics will be presented by treatment group. For continuous variables, the number of observations (n), mean, standard deviation, median, minimum, and maximum will be provided. For categorical variables, the frequency and percentage in each category will be displayed.

For summary statistics, the mean and median will be displayed to one decimal place greater than the original value and the measure of variability (e.g. standard deviation) will be displayed to two decimal places greater than the original value. All analyses will be performed using SAS® Version 9.3 or higher.

Descriptive statistics will be provided for each treatment group (ETX2514SUL and placebo [background imipenem/cilastatin therapy]). Statistical tests and/or confidence intervals (CIs) will be used to compare treatment groups.

